Data from throughout the study will be cross-referenced to develop the affirmative and sceptic briefs required for the HSCED. Pseudonyms will be used for the participants and there will be no patient identifiable information within the briefs. Once completed, the briefs will be sent to the expert panel of three Clinical Psychologist, with relevant interest and experience of psychotherapeutic change methods. The panel adjudicate over the case material using a semi-structured questionnaire to decide whether the client made a substantial change and where they attribute this towards (ACT-specific, non-specific, or extra-therapeutic factors). This process allows for a reduction in researcher bias.

SCHEDULE OF PROCEDURES

Procedures	Visits									
	Psychology Screening Assessment & Baseline 1 (wk1)	Baseline 2 (wk2)	Baseline 3 (wk3)	Baseline 4 & Session 1 - pre (wk4)	Sessions 2-5 (wks 5-8)	Session 6 - mid (wk 9)	Sessions 7-11 (wks 10-14)	Session 12 - post (wk 15)	Change Interview (wk 16)	Six wk follow-up (wk 20)
Informed consent	x									
Symptom, & process measures	x	x	x	x		x		x		x
Demographics	x									
Medical history	x						x			
ACT intervention				x	x	x	x	x		
Session, change, & fidelity measures				x	x	x	x	x		
Change Interview									x	

Note: wk = week; see Timetable of Measures for outline of when individual measures are administered.

WITHDRAWAL

Participants may be withdrawn from the trial either at their own request or at the discretion of the Investigator. The participants will be made aware that this will not affect their future care. Participants will be made aware (via the information sheet and consent form) that should they withdraw the data collected to date may not be erased in accordance with the University's Research Privacy Notice and information given in the Participant Information Sheet and may still be used in the final analysis.

Stopping rules and discontinuation:

- If a participant withdraws consent to continue.
- If a participant expresses that the intervention is causing their anxiety and depression to get worse.
- If a participant's physical health significantly deteriorates to a point where continuation would be impractical or create sufficient negative burden on them.
- If a participant fails to comply with the intervention.
- If new findings become published regarding likely risks or negative effects of ACT.

Should any of these criteria be met, the decision of whether the participant receives further support from the MHSOP will be decided by [name] and the wider MDT at the MHSOP. A replacement participant will be recruited, dependent of timeframe and ability to deliver therapy. Should criteria apply to all participants (such as evidence of the negative effects of ACT), the study as a whole will be temporarily stopped on ethical grounds. Interim analysis would be performed at this point to determine any negative effects of the intervention on the participants. Continuation of the study would be dependent on further guidance from the REC, NHS R&D and any other relevant parties.

ETHICAL AND REGULATORY CONSIDERATIONS

ASSESSMENT AND MANAGEMENT OF RISK

This study aims to reflect usual clinical practice where possible; therefore, the burden to participants will be of a similar level to treatment as usual. That is, they will be expected to attend one-to-one psychotherapy (either face-to-face or at distance) and to discuss their mental health difficulties; what contributed towards the development of their difficulties; and what is maintaining their difficulties. As with any psychological therapy, there is a potential risk that talking about distressing experiences will cause an increase in frequency or intensity of pre-existing mental health conditions.

These risks will be monitored through the study by the Trainee Clinical Psychologist (who is both researcher and therapist) through discussion with the participant, use of outcome measures and importantly by utilising weekly clinical supervision with [name] (Clinical Psychologist for the MHSOP). This allows a space for any concerns to be raised and for [name] to have clinical oversight of the participants. As part of standard clinical practice, and local NHS Trust policies, each participant will have a clinical risk assessment with the MHSOP. This will be reviewed by the researcher/therapist with [name] before starting therapy. Any relevant information will also be added to this, should anything relevant come up in therapy sessions.

The aspects of the study which are additional to usual practice are as follows: participants will be required to complete more questionnaires; participants will be required to come in for an interview after the block of therapy has ended. Every effort has been made to reduce the burden the questionnaires place upon participants. For instance, shorter questionnaires have been used where possible. Participants will also be asked about any adaptations required to complete questionnaires (e.g. larger font, someone completing questionnaires with them). Clients will be reimbursed for the aspects of the study which are additional to usual practice.

The interviews in this study may include sensitive topics; however, there are no anticipated adverse events for participants. Should there be an increase in intensity of mental health difficulties then any immediate risk will be discussed in sessions. The study will follow the Safeguarding policies and procedures of Nottingham Healthcare NHS Foundation Trust (the hosting Trust). In line with these procedures, should participants disclose anything to indicate that they or someone they know are at risk of harm, the researcher has a duty to report this. Participants will be informed of this where relevant and possible.

Once participants have finished with the research aspects of the study, participants will either be discharged from the MHSOP or continue to receive support. This will be dependent on the client's progress, any emergence of risk etc. Final clinical decision will be made by [name], Clinical Psychologist/Field Research Supervisor, at the MHSOP.

There are minimal risks to the researcher associated with this study, although therapy sessions may involve hearing distressing and emotive topics. The researcher will utilise both clinical supervision (through the MHSOP) as well as ACT focused supervision (through the University of Lincoln) to manage and monitor this.

Individual participant medical information obtained as a result of this study are considered confidential and disclosure to third parties is prohibited with the exceptions noted. Medical information may be given to the participant's medical team and all appropriate medical personnel responsible for the participant's welfare.

If information is disclosed during the study that could pose a risk of harm to the participant or others, the CI will discuss this with the Field Research Supervisor in the first instance and where appropriate report accordingly.

ADVERSE EVENTS

An adverse event (AE) is any untoward medical occurrence in a study participant. An adverse event (AE) may therefore be any unfavourable and unintended sign (including an abnormal laboratory finding), symptom, or disease that develops or worsens during the study period.

An AE may include:

- Exacerbation of a chronic or intermittent pre-existing condition including either an increase in frequency or intensity of the condition.
- Significant or unexpected worsening or exacerbation of the condition/indication under study.
- A new condition detected or diagnosed after study therapy administration even though it may have been present prior to the start of the study.

- Pre- or post-treatment events that occur as a result of protocol-mandated procedures (e.g., invasive protocol-defined procedures, modification of a patient's previous treatment regimen).

An AE does **not** include:

- Medical or surgical procedures (e.g., colonoscopy, biopsy). The medical condition that leads to the procedure is an AE.
- Social or convenience hospital admissions where an untoward medical occurrence did not occur.
- Day to day fluctuations of pre-existing disease or conditions present or detected at the start of the study that do not worsen.
- The disease/disorder being studied, or expected progression, signs, or symptoms of the disease/disorder being studied unless more severe than expected for the patient's condition.

Adverse events of participation in this study may be: there are no anticipated adverse events for participants associated with this study.

A serious adverse event (SAE) means any adverse event, adverse reaction or unexpected adverse reaction, respectively, that:

- a. results in death,
- b. is life-threatening,
- c. requires hospitalisation or prolongation of existing hospitalisation,
- d. results in persistent or significant disability or incapacity, or
- e. consists of a congenital anomaly or birth defect

Other 'important medical events' may also be considered serious if they jeopardise the participant or require an intervention to prevent one of the above consequences.

NOTE: The term "life-threatening" in the definition of "serious" refers to an event in which the participant was at risk of death at the time of the event; it does not refer to an event which hypothetically might have caused death if it were more severe.

There are no serious adverse events anticipated with participating in this study.

Participant reporting of adverse events

The Investigator will review all documentation (e.g., hospital progress notes, laboratory, or diagnostic reports) relative to the event being reported. The Investigator or clinician will then record all relevant information regarding an AE/SAE. All adverse events will be recorded and closely monitored until resolution, stabilisation, or until it has been shown that the study treatment / intervention is not the cause.

Participant removal from the study due to adverse events

Any participant who experiences an adverse event may be withdrawn from the study at the discretion of the Investigator.

ETHICS REVIEW AND COMPLIANCE

The study shall not commence until the study protocol, information sheets and consent forms have been reviewed and approved from a Research Ethics Committee and relevant NHS/Social Care permission is obtained

The sponsor will be responsible for deciding whether amendments are substantial and non-substantial in collaboration with the Chief Investigator.

Where an amendment is required to study documentation that required REC approval, changes will not be implemented until REC approval and HRA categorisation is received. Where an amendment requires local approval, this shall be sought prior to the amendment be implemented at each site in accordance with the categorisation given on the HRA approval letter.

Should an amendment be required to eliminate an apparent immediate hazard to participants this may be implemented immediately and the REC/HRA and R&D will be notified as soon as possible.

Minor amendments for logistical or administrative purposes may be implemented immediately

Amendments will be logged on the Sponsor's Study Amendment Log and stored in the Trial Master/Site File(s).

Annual Progress Reports shall be submitted to the REC within 30 days of the anniversary date on which the favourable opinion was given – until the end of the study.

A final report shall (where possible) be submitted to the REC within one year after the end of the study.

If the study is terminated prematurely the CI will notify the REC, including the reasons for premature termination.

PEER REVIEW

As part of the requirements for the DClinPsy course, this research has been through a number of stages in order to check it meets scientific quality. Two academic research staff, one from the University of Nottingham and one from the University of Lincoln, have formally reviewed the project protocol. The outcome was that it is of pass standard, feasible and of clinical importance. Progress since submission of the protocol to the course (May 2019) was assessed at the Research Annual Review (October 2019), where it was agreed that the research was progressing to the sufficient level. Prior to submission for IRAS approval for the study has also been sought from the Sponsor of the research (University of Lincoln) and Trust R&D where the research will take place (Nottinghamshire Healthcare NHS Foundation Trust). IRAS will also involve review by a REC panel. Once the study has finished, the same academic research staff will mark the Thesis before submission of journal article to a peer-reviewed journal. This study will also be supported by the research team to ensure academic quality.

PUBLIC & PATIENT INVOLVEMENT

Participants will be provided a summary of the main findings from the study, should they request this when asked at the end of the study. A summary of the findings will also be presented to the Mental Health Service for Older People (MHSOP), where the study will be carried out. As the project is part of a Doctoral Thesis, a manuscript of the thesis will be stored on the University of Lincoln Repository, along with any journal articles that result from the study.

PROTOCOL COMPLIANCE

Accidental protocol deviations may occur at any time. Accidental protocol deviations will be adequately documented on the relevant forms and reported to the Chief Investigator and Sponsor immediately.

Therapy will use the ACT treatment protocol suggested by Petkus and Wetherell (2013), detailed above. However, this is only a guideline and may be adapted based on participant factors. As ACT is a processes-based therapy, rather than a single manualised procedural treatment, adherence to a strict protocol is not theoretically mandated (Hayes & Hoffmann, 2017). Hayes & Hoffmann, 2017). Content of all sessions will be noted so that later process-change analyses can be performed.

Deviations from the overall study protocol which are found to frequently recur are not acceptable, these will require immediate action and could potentially be classified as a serious breach.

DATA PROTECTION AND PATIENT CONFIDENTIALITY

All study staff and investigators will comply with the principles of the Data Protection Act (2018) in protecting the rights of study participants with regards to the collection, storage, processing and disclosure of personal information and will uphold the Act's/Regulations core principles.

Each participant will be assigned a study identity number, for use on CRFs other trial documents and the electronic database.

Personal data, research data and the linking code will be stored in separate locations. When stored electronically, this will include using encrypted digital files within password protected folders and storage media. Personal information shall be stored separately to research data and will be kept secure, and maintained.

Personal data will be stored for six months following the end of the study, so that the Chief Investigator may provide participants with a summary of the research (should they wish to receive a copy).

Data generated as a result of this study will be available for inspection on request by the participating physicians, the University of Lincoln representatives, the REC, local R&D Departments and the regulatory authorities.

INDEMNITY

Insurance and indemnity for trial participants and trial staff is covered within the NHS Indemnity Arrangements for clinical negligence claims in the NHS, issued under cover of HSG (96)48. There are no special compensation arrangements, but trial participants may have recourse through the NHS complaints procedures.

The University of Lincoln as research Sponsor indemnifies its staff, research participants and research protocols with both public liability insurance and clinical trials insurance.

ACCESS TO THE FINAL DATASET

In compliance with the ICH/GCP guidelines, regulations and in accordance with the University of Lincoln Code of Practice for Research, the Chief or local Principal Investigator will maintain all records and documents regarding the conduct of the study. These will be

retained for at least five years or for longer if required. If the responsible investigator is no longer able to maintain the study records, a second person will be nominated to takeover this responsibility.

Copies of the Trial Master File and trial shall be archived at secure archive facilities at the University of Lincoln. This archive shall include all trial databases, including transcripts of audio files and associated meta-data encryption codes.

Personal data (such as contact details) will be destroyed after it is no longer necessary to contact a participant. Research data (including the consent form) will be retained for a period of five years following first publication. Recordings should be anonymised and archived with the research data as source data.

DISSEMINATION POLICY

The data custodian will be the Chief Investigator on behalf of the University of Lincoln.

This study will be completed as part of a Doctoral Thesis in Clinical Psychology. A manuscript of the Thesis will be available from the University of Lincoln Repository. The Thesis manuscript will include a journal article which will be submitted for peer review, as well as extended information on relevant aspects of the study (e.g. methodology, design). The journal article will be submitted to the Journal of Contextual Behavior Science (JCBS), with anticipated date of July 2021.

A summary of the main findings will be disseminated to participants involved in the study, should they indicate interest when asked. A summary will also be provided to the Mental Health Service for Older People that are hosting the research.

Findings from the study will also be presented at any relevant conferences (e.g. related to Older Adults or Acceptance and Commitment Therapy), should there be an opportunity to do so. This would usually be in the form of a poster.

REFERENCES

- Age UK. (2017). *Briefing: Health and care of older people in England 2017*. Retrieved from https://www.ageuk.org.uk/Documents/EN-GB/For-professionals/Research/The_Health_and_Care_of_Older_People_in_England_2016.pdf?dtrk=true
- Andresescu, C., & Reynolds, C. F., 3rd. (2011). Late-life depression: evidence-based treatment and promising new directions for research and clinical practice. *The Psychiatric Clinics of North America*, *34*(2), 335. <http://dx.doi.org/10.1016/j.psc.2011.02.005>

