3. Client's (qualitative) views on individual therapy sessions assessed with the Helpful Aspects of Therapy form (HAT; Lewlyn, Elliott, Shapiro, Firth, & Hardy, 1988). Completed by therapist in discussion with participant.

Fidelity measure

1. Adherence to ACT related processes assessed with the ACT Fidelity Measure (ACT-FM; O'Neill, Latchford, McCracken & Graham, 2019). Completed by therapist and secondary researcher.

EXPLORATORY OUTCOMES

Adaptations made to treatment will be recorded so that commentary can be made on what adaptations to ACT may be beneficial for older adult clients. **Consideration of the impact that delivering the intervention in a remote manner will also be made and any adaptations that were made to facilitate this.**

TABLE OF OUTCOMES

Objectives	Outcome Measures	Timepoint(s) of evaluation of this outcome measure (if applicable)
Primary Objectives	1. Quality of life (OPQOL-brief).	1. Baselines, pre-, mid- and post-intervention, and at six-week follow up.
Secondary Objectives	Symptom measures 1. Cognitive functioning (MoCA). 2. Changes in levels of anxiety and depression (HADS).	1. At initial contact, by service as standard practice. 2. At initial contact, by service as standard practice. Baselines, pre-, mid- and post-intervention,

		and at six-week follow up.
	Change measures 
 1. Client's goals (PQ). 2. Client's view on change (Change Interview). 	
 1. Prior to each weekly treatment session. 2. One week after finishing treatment.
	Process measure 
 1. Psychological flexibility (CompACT-8). 	
 1. Baselines, pre-, mid- and post-intervention, and at six-week follow up.
	Session measures 
 1. Quality of life/general outcomes (ORS). 2. Therapeutic alliance (SRS). 3. Client's views on the therapy session (HAT). 	
 1-3. At the end of each weekly treatment session.
	Fidelity measures 
 1. Fidelity of treatment (ACT-FM). 	
 1. At the end of each session (by therapist) and random sampling of all sessions (by Secondary Research Supervisor).

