To facilitate the cross-referencing of rich case records, several methods of analysis will be employed, dependent on the evidence area required for the affirmative or sceptic brief. These are outlined in Tables 1 and 2, respectively. All analyses will be completed using SPSS (Version 25.0; IBM Corp, 2017) or Microsoft Excel (Version 15.0.5179.1000; Microsoft Corporation, 2013). Analyses will be performed by the student researcher/therapist either at the MHSOP or the Universities of Lincoln or Nottingham. No data containing confidential information will be analysed outside of the MHSOP, in line with relevant NHS Trust policies.

Table 1		
Direct evidence for links between therapy process and outcome, from Elliott (2002).		
Direct evidence area	Description	Method of evaluation (specific analysis method)
1. Retrospective attribution	Change attributed by client to the therapy	Content of Change Interview (Framework Analysis)
2. Process-outcome mapping	Content of post-therapy changes correspond to specific processes within therapy	Correlations between within therapy measures (HAT), and quantitative outcome measures (Pearson correlation, or Spearman correlation if assumptions of normal distribution not met).
3. Within-therapy process-outcome correlation	In-therapy process variables covary with week-to-week changes in client problems	Correlations between ACT adherence and ORS, and the change questionnaire (i.e. the SPQ; Pearson/Spearman correlation)
4. Early change in stable problems	Therapy coincides with changes in long-standing client problems	Change in outcome measures from baseline to initial sessions (Pearson/Spearman correlation, visual analysis)
5. Event-shift sequences	Important events precede stable shifts in client problems, especially if therapy process and client change are logically related	Correspondence between within therapy measure (HAT) and variation in patient's problem (SPQ; Pearson/Spearman correlation, visual analysis)

Note: HAT – Helpful Aspects of Therapy form. SPQ – Simplified Personal Questionnaire.

Table 2

Evidence for links between nontherapy processes and outcome, from Elliott (2002)

Nonchange/ nontherapy area	Changes are...	Method of evaluation (analysis method)
1. Non-improvement	Either trivial or negative.	Assess reliable and clinical significance on measures (RCI calculations); ask ppt the importance and direction of any change (Change Interview).

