Up to 12 therapeutic sessions will be offered, delivered by the student researcher/therapist. At session 1 (week 4), confidentiality will be reiterated, including under what circumstances confidentiality would be broken (risk to them or others). They will also be explained the procedure of clinical supervision from [name] as well as ACT-supervision from [name] (the latter supervision not using confidential information). Participants will then be supported to complete the Simplified Personal Questionnaire (SPQ), noting their expectations for therapy, the main problems they are bothered with and duration of these. Participants will then be introduced to the underlying concepts of ACT, before starting with the proposed ACT-protocol (adapted from Petkus & Wetherell, 2013):

ACT area	Sessions and content
Values	Sessions 1-3 1. Regaining contact with values: What matters? 2. The role of religion 3. Making the most of the remaining time
Acceptance/Willingness	Sessions 4-5

	
 1. What's worked? What hasn't? What are the costs? 2. Control is the problem 3. Experiencing vs. avoiding 4. How does this fit with values?
Defusion	
Sessions 6-7
 
 1. Awareness of internal experiences 2. A thought is just a thought 3. Having a thought vs. content of a thought 4. Defusion from damaged conceptualized self
Mindfulness and Self as Context	
Sessions 8-9 (Mindfulness exercise conducted at the beginning of every session)
 
 1. Being in the present moment 2. Not judging thoughts or feelings 3. Thoughts and selves
Committed Action	
Begins during the Values sessions and continues throughout the intervention, but is emphasized during Sessions 10-12
 
 1. What goals are consistent with values? 2. What actions work toward these goals? 3. Breaking it down into steps 4. Problem-solving potential barriers 5. Enlisting support
Therapeutic blueprint	
Session 12
 
 1. Summary of the content 2. Review of SPQ and any change experienced 3. Next steps and further support options

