Therapy will use the above protocol as a guide for treatment; however, duration and content will be adapted based on the individual. Primarily this will be using extra sessions to focus on any content that participants may need further work with, but could also include a break in the middle of sessions. Sessions will predominantly be weekly and one hour in length, dependent on any required adaptations. Sessions will be delivered either over telephone or via QHealth. As ACT is a processes-based therapy, rather than a single manualised procedural treatment, adherence to a strict protocol is not theoretically mandated (Hayes & Hoffmann, 2017).

The basic structure of each session will be:

1. Participant completes weekly Personal Questionnaire before session.
2. Session begins with a mindfulness exercise.
3. Homework and concepts from previous session are reviewed.
4. New material for the session is covered.
5. Homework is assigned.
6. Therapist completed HAT with participant.
7. Participant is supported to complete ORS and SRS.

Following each session, the student researcher will receive clinical supervision with [name] by (secure) videocall or telephone to discuss any relevant case information, such as

risk and progress. A clinical note will be made on the participant's electronic case record, as in standard practice. The student researcher will also receive regular ACT supervision from [name], Secondary Research Supervisor/Chief Investigator to address any modality specific questions or dilemmas. Relevant discussions from this will be added to the participant's electronic case record as required.

At mid-point in therapy (usually session six), QP1.1 will be repeated at the start of the therapy session. QP1.1 will also be repeated at the final therapy session to act as the post-therapy time point.

During the final session, the PQ will be re-administered to determine whether there has been any change in their problem areas. Participants will also be given the opportunity to 're-author' their problem areas. This is to capture any theoretical change they may have occurred in identifying where problems at situation, as would be posited by the ACT theoretical framework (living with problems, rather than eliminating them). Participants will complete any required session questionnaires prior to filing in the PQ.

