The final session will also cover a summary of the sessions, as well as providing the participant with a therapy blueprint of what they specifically found useful. This will include any next steps for the participant (e.g. whether they will continue to be seen by the MHSOP) and what the process is for them to follow if there is a deterioration in mental health. The participant will be reminded of the data processing details and asked again if they would like a summary of the findings from the study.

One week after the final session, participants will complete a Change Interview, facilitated by [name], Trainee Clinical Psychologist, either face-to-face or by telephone/videocall, depending on the social distancing restrictions at the time. The Change Interview is a semi-structured interview to determine whether the client experienced change during the treatment, what they attributed this towards (e.g. therapeutic factors, external factors). The Change Interview is completed by a member of the research team the participant has not had previous contact with (to encourage more honest responses), and will be recorded on a NHS encrypted device so that the answers can be transcribed at a later date. The participants will then receive reimbursement towards their travel (if applicable) and for the factors of research which were additional to normal clinical treatment (extra questionnaires, attending Change Interview).

One month following the Change Interview, participants will be called up again by the Assistant Psychologist to complete QP 1.1. This will act as six-week post-therapy follow-up.

Following final therapy sessions, a secondary member of the research team (likely to be the Chief Investigator) will complete fidelity checks to ensure that the modality (ACT) is sufficiently adhered to. This will be conducted using a random sampling method and the researcher will have access to anonymised audio files, stored on an encrypted NHS Trust device.

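### The client's own problem ratings (PQ) end in the final session, so shifts after the last two sessions cannot be shown to be stable and maintenance on those problems is not measured

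*Combined protocol and SAP*

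**What the plan says.** The PQ is set up in session 1 (Study Regimen, Therapeutic sessions). After that, the Table of Outcomes places it "Prior to each weekly treatment session", and the session structure agrees: "Participant completes weekly Personal Questionnaire before session".

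The last administration is in the final session: "During the final session, the PQ will be re-administered to determine whether there has been any change in their problem areas". In the same place the protocol adds: "Participants will also be given the opportunity to 're-author' their problem areas".

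In the Schedule of Procedures, the row "Session, change, & fidelity measures" is marked for sessions 1 to 12 only (weeks 4 to 15). The row for symptom and process measures runs on to week 20. One week after therapy there is the Change Interview, described as a semi-structured interview with no PQ rating. Then: "One month following the Change Interview, participants will be called up again by the Assistant Psychologist to complete QP 1.1". The Table of Outcomes gives OPQOL-brief, HADS and CompACT-8 a follow-up time point, but not the PQ.

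Table 1 row 5 in Data Analysis defines the evidence sought as "Important events precede stable shifts in client problems" and reads it by setting HAT events against variation in the SPQ.

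**The concern.** Stability needs at least one reading after the one that first shows the shift. Because the PQ series ends with therapy, the last sessions have too few later readings for row 5. Those sessions are not incidental: the session plan puts its emphasis on Committed Action in sessions 10 to 12. The final reading may also be the least comparable, because items can be rewritten then. The wording suggests that the original items are re-rated and that re-authoring is additional, but it does not say so outright.

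The adjudicators would then see late improvement on the most individual measure without being able to tell a lasting change from a high at the end of therapy. Two contacts after therapy already exist, both run by someone other than the therapist, and neither is described as taking the PQ.

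**Working it through.** The plan gives no figure on this point, so the check is a count of occasions.

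**Inputs.** Session 1 is in week 4 and session 12 in week 15, so session k falls in week k + 3 (Schedule of Procedures). The PQ is taken before each session. HAT events are recorded at the end of each session. The Change Interview is in week 16 and the follow-up call in week 20.

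**Formulas.** For an event in session k of 12:
- later PQ weeks = 12 − k;
- confirming weeks, beyond the one that first shows the shift = max(0, 12 − k − 1);
- adding week 20 raises the later readings by 1, and adding weeks 16 and 20 raises them by 2.

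**Results.** Each cell gives later readings, then confirming readings in brackets.

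| Event in session | Week | As planned | Plus week 20 | Plus weeks 16 and 20 |
|---|---|---|---|---|
| 1 | 4 | 11 (10) | 12 (11) | 13 (12) |
| 9 | 12 | 3 (2) | 4 (3) | 5 (4) |
| 10 | 13 | 2 (1) | 3 (2) | 4 (3) |
| 11 | 14 | 1 (0) | 2 (1) | 3 (2) |
| 12 | 15 | 0 (0) | 1 (0) | 2 (1) |

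The count is by week. The final session may hold two PQ ratings on one day, one before it and one during it. The second gives a session-11 shift a same-day repeat and a session-12 event a same-day reading. Neither speaks to persistence over time.

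**Time observed after therapy.** PQ: 15 − 15 = 0 weeks as planned, and 20 − 15 = 5 weeks with the follow-up reading. (The call is labelled a six-week follow-up but falls five weeks after session 12 on the schedule; that label and the schedule should be reconciled separately.)

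**Could the PQ be inside QP1.1?** The contents of QP1.1 are not listed, and the Timetable of Measures that the schedule refers to is not in the text available. Inclusion is very unlikely. QP1.1 is first given at Baseline 1 in week 1, three weeks before the PQ is set up in week 4, and the account of the end of therapy treats the two as separate instruments.

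**Sample size.** The target is not affected: 3 / (1 − 0.25) = 4, which matches the plan's maximum of four participants.

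**The case against.** The best reply is that the PQ is meant as a within-therapy measure and does that job. Most of this stands.

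- A reader might infer that the first guiding question goes unanswered. It does not: that question is limited to change during the intervention, which the session 1 to 12 ratings cover. Maintenance of goal change is not a named objective.
- A reader might infer that row 5, or Table 1 generally, is undermined. Events in sessions 1 to 9 have ample later readings. Row 3 pairs process with problems week by week, so it gains nothing from ratings after therapy. Row 5 is one of five areas, and evidence in two is enough for adjudication.
- A reader might infer that durability is not assessed at all. OPQOL-brief (the primary outcome), HADS and CompACT-8 are repeated at follow-up, and the Change Interview gives a qualitative account at one week. None of these is described as re-rating the client's own problems, so the gap remains for the PQ.
- A reader might infer that the PQ is always rated under the therapist's guidance. The Secondary Outcomes list mentions guidance, but the session structure has the participant completing the weekly form beforehand and reserves the mention of support for the ORS and SRS. Guidance at every rating is not established.
- Averaging later ratings with the last one might seem to sharpen the end-state estimate. That assumes the stability in question, and averaging sessions 10 to 12 would give the same gain.
- Making persistence to week 20 the test of stability would be wrong. A shift that held through therapy could be reversed by a later bereavement or illness, which Table 2 rows 6 and 7 treat as separate influences.

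The protocol also aims to limit questionnaire burden, and a rating just before the Change Interview could prime the client's account. Both points shape the fix.

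**Conclusion.** The point holds in limited form. No PQ rating is scheduled in the five weeks between the last session and the follow-up call. Stability cannot be confirmed for events in sessions 11 and 12 (no confirming PQ week in either case) and rests on one confirming week for session 10. Maintenance on the client's own problems is not measured. Shifts from sessions 1 to 9 and the follow-up of the primary outcome are not affected.

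This is a gap in one secondary measure that can be closed cheaply; it does not put the primary objective at risk. The conclusion assumes 12 weekly sessions as scheduled and that QP1.1 does not contain the PQ. If therapy is shorter, the same gap falls on whichever sessions come last.

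**What to change.** Add the original, un-rewritten PQ items to the week-20 Assistant Psychologist call. This gives one reading after therapy, taken by someone other than the therapist, and lifts the confirming readings for events in sessions 10 and 11 from 1 and 0 to 2 and 1. An event in session 12 gains its first later reading but still has no confirming one. If that matters, also take the PQ at the week-16 contact, after the Change Interview so that it does not prime the answers; session 12 then has one confirming reading.

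State in the analysis text that the added reading is evidence on maintenance and on the stability of late shifts, to be read alongside extra-therapy events and medication or health changes (Table 2 rows 6 and 7). It should not be a pass or fail rule for shifts already shown to hold during therapy. State also that the original items are re-rated at the final session even where a participant re-authors them.

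Cost: a few minutes of questionnaire burden in a contact that already exists (two contacts if week 16 is used), and a protocol amendment for the sponsor and Chief Investigator to classify. Therapy and sample size do not change.
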